6.1 DETERMINATION OF SAMPLE SIZE

A sample size of 56 subjects was chosen to obtain 48 evaluable subjects. Subjects are evaluable if ECGs are available for all three periods to allow (1) the derivation of the primary endpoint (i.e., change from baseline on Day 14), and (2) the assessment of the effect of moxifloxacin.

Based on the calculation of the sample size for a TQT study (Zhang and Machado, 2008)⁶, assuming a 1-sided 5% significance level and a within-subject SD of 8 ms for $\Delta QTcF$ and a true mean difference of 3 ms in $\Delta QTcF$ between balovaptan and placebo, a sample size of 48 evaluable subjects who complete the study will provide a power of 96.6% to demonstrate that the upper bound of all the 2-sided 90% CIs on $\Delta\Delta QTcF$ will fall below 10 ms for up to 7 post-dose time points (0.5, 1.25, 2.5, 4, 8, 12 and 24 hours).

Sample Size Determination for Assay Sensitivity:

Based on the calculation of the sample size for a TQT study from Zhang and Machado, 2008⁶, as the test is performed at three time points separately (1.25, 2.5, and 4 hours), a one-sided 5% significance level (with adjusted one-sided significance levels of 5%, 2.5% and 1.67%) is used along with a within-subject SD of 8 ms for $\Delta QTcF$, a sample size of 48 evaluable subjects who complete the study will provide a power of 99% to prove a mean difference of 5 ms in $\Delta QTcF$ between moxifloxacin and placebo (i.e., $\Delta\Delta QTcF$) at $1 \geq$ of the 3 specified time points.

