6.7.3 By-Time Point Analysis

The statistical hypothesis to be tested for the primary assessment of QT prolongation for each dose of the balovaptan treatment is:

$$H_0: \cup \{\mu_{D(i)} - \mu_{P(i)}\} \geq 10, i = 1, 2, \dots, 7$$

$$H_1: \cap \{\mu_{D(i)} - \mu_{P(i)}\} < 10, i = 1, 2, \dots, 7$$

where $\mu_{D(i)}$ and $\mu_{P(i)}$ are the least squares (LS) mean of Δ QTcF for each dose of balovaptan and placebo at time point i on Day 14, respectively.

The “by-time point” analysis for QTcF will be based on a linear mixed-effects model with change-from-baseline QTcF (Δ QTcF) as the dependent variable; gender, period, sequence, time (categorical), treatment (balovaptan, and placebo), and time-by-treatment interaction as fixed effects; and baseline QTcF as a covariate. An unstructured covariance matrix will be specified for the repeated measures at time points for subject within treatment period. If the model with an unstructured covariance matrix fails to converge, other covariance matrices such as compound symmetry and autoregressive will be considered. If the fixed effects for period and/or sequence should prove to be nonsignificant (i.e., if the p value > 0.1), these effects may be removed from the model.

and the analysis will be repeated without those covariates. From this analysis, the LS mean and 2-sided 90 % CI will be calculated for the contrast “balovaptan versus placebo” at each dose of balovaptan and each post-dose time point on Day 1 and Day 14, separately. If the upper bound of the CI lies below 10 ms for the highest dose group of balovaptan at all seven post-dose time points (0.5, 1.25, 2.5, 4, 8, 12, and 24 hours) on Day 14 (steady state), balovaptan will be concluded not to have a significant effect on QT interval prolongation.

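### The primary QTcF model may drop period and sequence when p > 0.1, so up to four models could supply the bound tested against 10 ms; the numerical effect is small and the remedy is free

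*Protocol*

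**What the plan says.** Protocol 6.7.3 models ΔQTcF with "gender, period, sequence, time (categorical), treatment (balovaptan, and placebo), and time-by-treatment interaction as fixed effects", plus baseline QTcF as a covariate. It then adds a screening rule. The trigger reads "If the fixed effects for period and/or sequence should prove to be nonsignificant (i.e., if the p value > 0.1". The consequence, when the trigger is met for either term, is that "these effects may be removed from the model". A page break splits the sentence at that point, and the text on the next page reads: "and the analysis will be repeated without those covariates. From this analysis, the LS mean and 2-sided 90 % CI will be calculated".

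Read as one passage, the fit without the removed terms appears to supply the confirmatory intervals. The protocol does not say that removal is compulsory, that the full model stays primary, or what happens when both terms qualify.

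The same model is reused for HR, PR and QRS (Protocol 6.7.4) and for moxifloxacin assay sensitivity (Protocol 6.7.5).

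The supplied SAP does not settle the matter. Section 5.0 leaves the cardiodynamic ECG analyses to a separate SAP by ERT, and section 7.1 reports no changes from the protocol.

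**The concern.** Period and sequence are design factors of the crossover, known before any data exist, so nothing has to be learned from the data to decide on including them. Here their presence in the primary model depends on p values from the trial itself. The word *may* then leaves the removal optional even when the rule is met. If *may* were read as *will*, the data would still choose among the models.

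The screening fit contains treatment, and sequence cannot be fitted without the randomisation codes, so the choice is made with treatment assignments in hand. The conclusion is a pass or fail on seven upper bounds against 10 ms, and a single specified model should produce those bounds. Because HR, PR, QRS and assay sensitivity reuse the model, each analysis could end with a different set of terms.

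**Working it through.** **The plan's power figure.** Protocol 6.1 gives the inputs: "assuming a 1-sided 5% significance level and a within-subject SD of 8 ms", "a true mean difference of 3 ms in" ΔQTcF, 48 evaluable subjects, and upper bounds that "will fall below 10 ms for up to 7 post-dose time points".

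- SE of the paired contrast = 8 × √(2/48) = 1.633 ms.
- Power at one time point for 10 − 3 = 7 ms, one-sided 5%, noncentral t with 47 df = 0.99505.
- Seven independent time points: 0.99505^7 = 0.9658, against the stated 96.6%.

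The figure reproduces without any period or sequence term, so fixing those terms leaves the planned power calculation unchanged.

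**Number of models.** Two terms, each kept or dropped, give 2² = 4 models. All four are open only if both p values exceed 0.1. If one does, two are open; if neither does, one.

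**Why the effect should be small.** Across the 12 sequences (Protocol 3.1), each of A, B and C/D falls in each period in 4 sequences. With equal, complete sequences, treatment is orthogonal to period and sequence, and dropping them hardly moves the contrast. Exact balance is not assured, however. 56/12 = 4.67 is not a whole number, 48 of 56 are expected to be evaluable, and the QT/QTc population (Protocol 6.7.1) admits subjects with one valid post-dose value.

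**Simulation at the boundary.** One binding time point, true effect 10 ms, within-subject SD 8 ms, 2,500 trials per row (4,000 in the first two). Assumptions not in the documents: between-subject SD of the change 5 ms; baseline SD 15 ms between and 6 ms within subjects; and the period effects, sequence effects and missing-data rates shown. Where a subject term was fitted, its variance components were treated as known. Missing means 7% of period 2 and 3 records.

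| Setting | All four open | Full model passes | Best eligible passes | Spread of upper bound, median / 95th percentile (ms) |
|---|---|---|---|---|
| n=48 complete, no effects, subject term | 84.1% | 5.03% | 5.17% | 0.043 / 0.110 |
| n=56, 7% missing, no effects, subject term | 82.4% | 5.63% | 6.05% | 0.081 / 0.223 |
| n=48 complete, period 0/1.5/3 ms, subject term | 48.0% | 5.04% | 5.20% | 0.038 / 0.103 |
| n=56, 7% missing, period 0/1/2 ms, sequence SD 2 ms, subject term | 50.4% | 4.88% | 5.00% | 0.064 / 0.224 |
| n=48 complete, no effects, no subject term | 51.2% | 2.92% | 3.00% | 0.024 / 0.098 |
| n=48 complete, period 0/1.5/3 ms, no subject term | 35.5% | 3.04% | 3.04% | 0.021 / 0.094 |
| n=56, 7% missing, period 0/1/2 ms, sequence SD 2 ms, no subject term | 23.6% | 2.80% | 3.08% | 0.030 / 0.231 |

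The largest increase is 6.05 − 5.63 = 0.42 points. The Monte Carlo standard error of each pass rate is about 0.3 to 0.4 points. Both columns use the same simulated trials, so their difference is less noisy than either rate.

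**Heavier dropout.** A second simulation used 56 subjects, 15% dropout without replacement, between-subject SD 0 or 5 ms, period effects 0 or 0/2/3 ms, and 1,500 trials per setting. The mean spread was 0.12–0.13 ms (95th percentile 0.29–0.33 ms). Picking the most favourable eligible model added 0.1–0.7 points to the false-pass rate, for example 5.1% to 5.7%. Without dropout the mean spread was 0.04–0.05 ms.

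**Assay sensitivity.** Moxifloxacin and its placebo come from one joint period per subject (Protocol 3.3.1.2 and 6.7.2). Sequences 5, 6, 11 and 12 put C or D in period 1; sequences 2, 4, 8 and 10 in period 2; sequences 1, 3, 7 and 9 in period 3. If only that period is analysed, sequence determines period. The design matrix has rank 13 (intercept, 11 sequence terms, treatment) with or without period.

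**The case against.** The strongest reply is that this is a prespecified rule, with two named terms and a numeric trigger, and that the governing ERT SAP has not been seen. Protocol section 6 requires the SAP to be final before database lock, so the choice may be closed there. That stands as a limit: nothing supplied shows that a model will be picked at will after unblinding. The protocol text still leaves the choice open and should agree with the ERT SAP.

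A second reply is that the effect is too small to matter. A spread of 0.1 ms compares with an SE of 1.633 ms. A further simulation (3,000 trials, 15% dropout, between-subject SD 5 ms, within-period covariance only) moved the pass rate from 2.6% to 2.7% at a true 10 ms, and from 99.3% to 99.4% at the planned 3 ms. Replacement, although discretionary, uses the same sequence (Protocol 4.2.1, SAP 6.2) and would help restore balance. All of this stands. A reader might infer a sizeable type I error problem from four competing models; the calculations do not support that.

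Two further inferences are tempting. One is that the screening p values ignore subject correlation across periods, because the only covariance stated is within treatment period. The protocol calls the model linear mixed-effects and neither names nor excludes a subject random effect, so this argues from silence, and keeping period and sequence would not repair it. The other is that both terms must be kept in the assay-sensitivity model. That fails if only the joint period is analysed, because period is then not estimable alongside sequence.

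**Conclusion.** The point holds as a gap in pre-specification. Up to four fixed-effects models could be primary, depending on the trial data and on how *may* is used. Its size is small: a mean spread in the upper bound of about 0.1 ms with 15% unreplaced dropout and about 0.05 ms without, and at most about 0.4 to 0.7 points on the false-pass rate if the most favourable eligible model is taken at a true 10 ms.

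These sizes rest on single-time-point simulations with the assumed between-subject SD, period effects and dropout stated above, and on the protocol without the ERT SAP. The count of four covers fixed effects only. The covariance fallback ("other covariance matrices such as compound symmetry and autoregressive will be considered") is a further open choice, but arises only if the unstructured matrix fails to converge. The point is a free improvement and does not threaten the trial's conclusion.

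**What to change.** - In Protocol 6.7.3, delete the sentence allowing removal and the repeat analysis without those terms. State that period and sequence stay in the primary QTcF model whatever their p values.
- Apply the same rule to the HR, PR and QRS models in Protocol 6.7.4.
- Label any reduced model a sensitivity analysis.
- For assay sensitivity (Protocol 6.7.5), fix the terms in advance as well. State whether all periods or only the joint moxifloxacin/placebo period enter the model; in the latter case, do not require both period and sequence.
- Make the ERT cardiodynamic SAP match.

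The cost is wording in two documents. Keeping both terms uses at most 2 + 11 = 13 degrees of freedom, and the 96.6% power calculation does not change.

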3.3 RATIONALE FOR STUDY DESIGN

The study will utilize a positive-control, 400 mg moxifloxacin, to assure study design and measurements will be able to detect potential ECG effects of balovaptan. Moxifloxacin, a fluoroquinolone antibiotic, when utilized at therapeutic doses (400 mg) is associated with QT prolongation and regulatory authorities have recommended it as a positive control to evaluate the sensitivity of clinical studies designed to detect small but significant increases in QT interval measurements.⁴

Across clinical trials, no balovaptan associated changes in blood pressure or HR are apparent. Therefore, this study uses QTcF as primary parameter rather than an individualized corrected QTc. Since a cross-over design corrects for diurnal fluctuations of QTc, a separate Day -1 reading is not needed, 3 time points (replicates at each time point) pre-dose are used as baseline.

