6.7.5 Assay Sensitivity

In order to confirm that the assay is sufficiently sensitivity to detect an effect, the following statistical hypothesis is tested for values recorded at the three pre-defined post-dose time points (1.25, 2.5, and 4 hours):

$$H_0: \cap \{\mu_{M(i)} - \mu_{P(i)}\} \leq 5, i = 1,2,3$$

$$H_1: \cup \{\mu_{M(i)} - \mu_{P(i)}\} > 5, i = 1,2,3$$

where $\mu_{M(i)}$ and $\mu_{P(i)}$ are the LS mean of Δ QTcF for moxifloxacin and placebo at time point i , respectively.

The analysis to show assay sensitivity will be based on the change-from-baseline post-dosing QTcF of moxifloxacin. The same model will be used as described for the primary analysis. For the 3 predefined time points (1.25, 2.5, and 4 hours post-dosing), the contrast in treatment $\Delta\Delta$ QTcF = “moxifloxacin - placebo” will be tested against the 1-sided null hypothesis $\Delta\Delta$ QTcF \leq 5 ms on the 5% level. Multiplicity will be controlled by using a Hochberg procedure.¹⁰ If after this procedure, the LS mean of $\Delta\Delta$ QTcF is significantly larger than 5 ms for at least 1 time point of these 3 time points, assay sensitivity will be considered shown. In addition, 2-sided 90% CIs will be obtained for the contrast at all time points and used in the figures.

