6.7.7 Concentration-QTc Analysis (Secondary Analysis)

The concentration-QTc analysis will be based on placebo-corrected change-from-baseline QTcF ($\Delta\Delta\text{QTcF}$). That is, for the placebo adjustment, the individual ΔQTcF for placebo calculated at a specific time point is subtracted from ΔQTcF for the same subject on balovaptan at the same time point to generate $\Delta\Delta\text{QTcF}$. The relationship between plasma concentrations of balovaptan and its metabolites (M2 [as appropriate] and M3) and $\Delta\Delta\text{QTcF}$ will be investigated by linear mixed-effects modeling.

A full model will include $\Delta\Delta\text{QTcF}$ as the dependent variable, time-matched plasma concentrations of each analyte (balovaptan, M2 [as appropriate] and M3) as the covariates, centered baseline QTcF as an additional covariate (i.e., baseline QTcF for individual subject at each post-dose time point subtracting the population mean baseline QTcF for all subjects), and subject as a random effect for both intercept and slopes, when applicable. Assay sensitivity may also be evaluated by a concentration-QTc analysis of the effect on $\Delta\Delta\text{QTcF}$ of moxifloxacin using a similar model as the above one.

The following model selection procedure among the full model and reduced models from possible first order combinations (without quadratic and interaction terms) among the three analytes (including models with only one analyte and with any two analytes) will be conducted by using Akaike Information Criterion (AIC) and the t-value for the intercept estimator.⁵ The selection will start from the full model and remove the analyte with the least significant slope from the model until only one analyte is left to evaluate the most appropriate model(s). Note that a significant intercept is not biologically plausible and therefore indicates model misfit. The selection of the final models will be performed among those models with an absolute t-value for the intercept estimate < 1.95 . Nonlinear models (Emax model) will be included in this set only if the test for linearity indicates non-linearity. Among these models, the model with the smallest AIC will be selected as primary. If none of the models qualify according to the condition on the t-value for the intercept estimator, non-linear models will be considered.

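### The protocol's rule for a negative QT conclusion rests on the 10 ms bounds alone and does not require that assay sensitivity be shown

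*Protocol*

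**What the plan says.** **The decision rule.** Protocol 6.7.3 has one condition and one consequence. The condition is: "If the upper bound of the CI lies below 10 ms for the highest dose group of balovaptan at all seven post-dose time points" on Day 14. The consequence is that "balovaptan will be concluded not to have a significant effect on QT interval prolongation". Moxifloxacin is not mentioned.

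**The control test.** Protocol 6.7.5 tests moxifloxacin minus placebo against 5 ms at three time points, with a Hochberg adjustment. If the effect is significantly above 5 ms "for at least 1 time point of these 3 time points, assay sensitivity will be considered shown". The section does not say what follows for balovaptan if it is not shown.

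**The purpose of the control.** Section 3.3 says moxifloxacin is used "to assure study design and measurements will be able to detect potential ECG effects of balovaptan". Section 6.7.5 opens with a similar aim. Section 6.1 counts a subject as evaluable only if the moxifloxacin effect can be assessed as well as the primary endpoint.

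**What happens on failure.** Section 4.5.10 has the moxifloxacin PK samples analysed only if the assay sensitivity test fails, and then uses them for an exposure-response analysis. Section 6.7.7 adds, without tying it to failure: "Assay sensitivity may also be evaluated by a concentration-QTc analysis of the effect on" QTcF of moxifloxacin. Neither section gives a pass criterion or a consequence for the balovaptan conclusion.

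**The SAP.** Section 5.0 leaves the cardiodynamic ECG analyses to a separate SAP by the ECG vendor. Section 9.4.3 plans no formal hypothesis testing.

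**The concern.** The primary claim is that an effect of 10 ms or more is absent. In such a trial, poor measurement does not work against the claim. Anything that shrinks recorded QTcF differences pulls the upper bounds down and makes the rule easier to satisfy. The positive control is the one element of the design that separates no effect from no ability to see an effect.

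The protocol states that purpose and then omits it from the sentence that draws the conclusion. If the control test failed and the ten-millisecond rule were met, 6.7.3 read literally would prescribe a negative conclusion that the trial's own control does not support. The fallback analysis has no criterion, so how to read such a trial would be settled after the results were known.

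**Working it through.** **Inputs.** Protocol 6.1, "assuming a 1-sided 5% significance level and a within-subject SD of 8 ms" for the change in QTcF; "a true mean difference of 3 ms" between balovaptan and placebo; 48 evaluable subjects; seven time points; stated power 96.6%. The stated power of the control test is 99%. The documents do not state the true moxifloxacin effect behind that figure.

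**1. Reproduce the stated power.**
- Standard error of a within-subject difference: 8 × √(2/48) = 1.633 ms.
- Distance from the assumed effect to the margin: 10 − 3 = 7 ms.
- Power at one time point, noncentral t with 47 df: 0.99505.
- Seven time points taken as independent: 0.99505^7 = 96.58%, which matches 96.6%.

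**2. An assay that records nothing (assumed measured difference 0 ms at every time point).**
- Half-width of the 90% CI: 1.678 × 1.633 = 2.74 ms.
- *10 ms rule.* An estimate must stay below 10 − 2.74 = 7.26 ms, which is 7.26/1.633 = 4.45 standard errors above 0. The chance of missing this at one time point is about 0.000006 (noncentral t). Over seven it is at most 7 × 0.000006 = 0.00004. The rule is met more than 99.9% of the time.
- *Control test.* Hochberg can reject only if at least one of the three p-values is 0.05 or less, so an estimate must exceed 5 + 2.74 = 7.74 ms, or 4.74 standard errors above 0. The chance is about 0.000002 per time point and at most 0.000006 over three. The control fails about 100% of the time.

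**3. Partial loss of signal (illustration).** Assumptions: true balovaptan peak 12 ms, with effects at the seven time points of 0.5, 0.8, 1, 1, 0.9, 0.8 and 0.7 of that peak; true moxifloxacin effect 10 ms at all three time points; correlation 0.5 between time points; the two tests independent.

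| Share of true effect recorded | 10 ms rule met | Assay sensitivity shown |
|---|---|---|
| 100% | 0.0% | 96% |
| 75% | 3.6% | 48% |
| 50% | about 60% | about 4% |
| 25% | 98.7% | about 0% |

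At 50% capture the rule as written gives a false negative conclusion about 60% of the time (82% to 22% for true peaks of 10 to 15 ms). Requiring both conditions cuts the figure for a 12 ms peak to about 0.60 × 0.04 = 2%.

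**4. What the extra condition would cost.**
- Whatever the dependence between the two tests, the chance of passing both is at least 0.966 + 0.99 − 1 = 95.6%. If they are independent it is 0.966 × 0.99 = 95.6%.
- A sound assay can fail the control by chance. On the stated 99% power this is about 1%. Simulated with Hochberg at the same standard error (estimated on 47 df), for assumed moxifloxacin effects equal at all three time points:

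| Assumed effect | Correlation 0 | 0.5 | 0.8 |
|---|---|---|---|
| 10 ms | 0.7% | 4.4% | 8.5% |
| 11 ms | 0.03% | 0.8% | 2.2% |

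At 12 ms the failure rate is at most 0.4%.

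**The case against.** The strongest reply is that the protocol plainly intends the control to govern interpretation. Assay sensitivity is a numbered secondary objective with its own endpoint and formal hypothesis, its purpose is stated, and evaluability depends on it. A failed test would be reported beside the balovaptan result, and any informed reader would discount the latter. ECGs are read centrally by blinded analysts, with up to ten replicates per time point, so an assay that records nothing is an extreme case. Finally, the document that defines the ECG analyses in detail is the vendor's SAP, which was not supplied.

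Much of this stands as a limit on the claim. A reader might infer that a trial with a failed control would certainly be reported as negative. The documents do not support that: the vendor's SAP may contain the link, and the failed test would itself be reported. Nor does the rule say balovaptan is free of any QT effect; its wording is the narrower absence of a significant effect on prolongation.

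The reply does not repair the rule. Section 6.7.3 is complete as written, and stating the control's purpose elsewhere does not add a condition to it. The partial-loss figures show that the problem does not need a total failure of measurement.

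Two further inferences should be resisted. The sound-assay failure rates in step 4 are the cost of adding the condition, not the harm of leaving it out, and they rest on an effect size that the documents do not give. And the concentration-QTc analysis cannot simply be barred from showing assay sensitivity, because 6.7.7 expressly allows that use. Its defect is the missing criterion.

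**Conclusion.** The point holds for the protocol text. Section 6.7.3 draws the negative conclusion from the 10 ms bounds alone, and nothing in the supplied documents makes it depend on assay sensitivity. It matters only when the control fails, but that is the case the control was included to catch. The 0 ms result rests on the protocol's SD and sample size and an assumed total loss of signal. The partial-loss figures rest on further assumptions about effect sizes, time course and correlation, and are illustrative. The stated alpha and the 96.6% are not in question. This should be corrected, subject to a check of the ECG vendor's SAP.

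**What to change.** 1. Amend 6.7.3 so that the negative conclusion requires both that assay sensitivity is shown under 6.7.5 and that all seven Day 14 upper bounds at the highest dose lie below 10 ms. State that the QT result is inconclusive if assay sensitivity is not shown.
2. For the fallback in 4.5.10 and 6.7.7, either prespecify the criterion by which the moxifloxacin concentration-QTc analysis would count as showing assay sensitivity, or label it supportive.
3. Check the ECG vendor's SAP for the same link, and mirror the wording there before unblinding.

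The cost is a few sentences. No extra subjects or procedures are needed, and the alpha and power of the 10 ms test are unchanged. The downside is that a sound trial whose control fails by chance becomes inconclusive, at the rates in step 4 of the working. A prespecified fallback criterion could recover some of those trials.
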